## **Study Protocol**

After the approval of the local ethics committee (Approval ID: 2014/18/05), medical records of patients who underwent surgery between 2010 and 2013 for Gartland type 3 fracture were retrospectively screened. Patients with pathological fractures, conservative follow-up, less than the 1-year follow-up, and patients with incomplete postoperative follow-up were excluded from the study. In the present study, the patients were divided into 5 groups according to the configurations of the K-wires in fixation as Group 1 (crossed 1 lateral 1 medial), Group 2 (crossed 2 lateral 1 medial), Group 3 (crossed 1 lateral 2 medial), Group 4 (2 lateral divergent), and Group 5 (3 lateral divergent). Closed reduction and percutaneous pinning were initially preferred in all patients. One hundred patients (68 males and 32 females) who underwent surgery for Gartland type 3 supracondylar humerus fractures were included in the study. 98% of the fractures are extension and 2% are flexion type fractures. The left humerus was affected by 73% and the right humerus in 27%. While 53% of the fractures occurred with a simple fall at home, 47% were outside. The distribution of demographic features and injury characteristics of the patients were presented in Table 1.

All patients evaluated at the emergency room and peripheral neurovascular examination were reported. The SCHF classified according to Gartland classification [5]. A long arm plaster used to immobilize the elbow in  $110^{\circ}$ - $120^{\circ}$  of elbow flexion in a comfortable position. No closed reduction was attempted in the emergency department. The timing of the surgeries was determined by the patients' condition and operating room availability. Open fractures with associated vascular injury were taken to the operating room emergently on presentation. Range of motion on the operated and non-operated side was evaluated at all controls and at final control measurements were statistically analyzed.

### ***Surgical technique***

Under general anesthesia, a high-arm tourniquet was placed on the arm, but not inflated and prepared for open reduction and fixation if needs. Intravenous cefazolin used for appropriate for patients' weight. The upper limb was prepared and dressed. Closed reduction was applied via manual traction. Then varus-valgus position checked by the surgeon by palpating the epicondyles and discussed with the preoperative images. While gradually flexing the elbow in extension type fractures (hyperextension can be used in some flexion type fractures), the surgeon pressed the olecranon to push the distal fragment in the sagittal plane to anteriorly for reduction. In pronation, we check fluoroscopy images on the coronal and sagittal plane (Figure 1). The reduction was considered acceptable when the anterior humeral line (AHL) bisected the middle third of the capitellum as observed on the lateral view and the humeral capitellar angle (HCA) was normal (range,  $9^{\circ}$ - $26^{\circ}$ ) on the AP fluoroscopy view [5,6].

Under fluoroscopy guidance, the first KW applied on the lateral epicondyle to the medially. For cross-wiring medial epicondyle was centered and KW applied medial to lateral. KWs were used for the fixation in different configurations such as 2 medial+1 lateral, 2 lateral+1 medial, 2 lateral, 3 lateral, or 1 medial+1 lateral. Mini-incision at medially to prevent iatrogenic ulnar nerve injury was used for the application of medial KW. Lateral KWs were preferred at divergent orientation. The surgeons who managed the operation used an adequate number of pins to fix the fracture with sufficient stability for all patients. Surgeons decided on the number and configuration of pins used in the intraoperative period. After the fractures are reduced, the first k-wire is applied laterally. They decided on the other KW in the intraoperative period according to the flexion-extension fluoroscopy images after the first KW. Most of the patients used cross KW 1L-1M and cross KW 2L-1M (Figure 1, Figure 2, and Figure 3). The pin number and orientation were determined entirely according to the configuration to achieve fixation stability during surgery. In the fractures where the arm is

edematous and the medial epicondyle cannot be palpated, the use of a lateral pin is preferred to avoid the risk of ulnar nerve injury. The pin diameter was determined according to the age of the patient and the cortical thickness of the humerus seen on the lateral radiograph. All patients evaluated clinically and radiologically at 2nd-, 4th- and 6th weeks, 3rd- and 6th months, and annually in the postoperative period (Figure 2 and Figure 4). The elbow was immobilized with a long arm plaster for 4 to 6 weeks. Plaster and pins were removed in the outpatient clinic after callus formation seemed (between 4th and 6th week). The passive range of motion exercises was started after the pin and plaster removed.

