### ***Statistical results***

Statistical analysis was performed with NCSS ( Number Cruncher Statistical System) 2007 (Kaysville, Utah, USA). Many Whitney U test was used for descriptive statistical methods evaluation (average, standard deviation, median, frequency, ratio, minimum, maximum) and not normally distributed data comparison. Kruskal Wallis test was used for not normally distributed three and upper groups quantitative data comparison. Mann Whitney U test was used for the definition of the different groups. Friedman test was used for the comparison of intragroup not normally distributed parameters and the Wilcoxon Signed Ranks test and Marginal Homogeneity test was used for evaluation of binary comparison. Fisher-Freeman-Halton test was used for qualitative data comparison. P values were considered statistically significant when  $p < 0.01$  and  $p < 0.05$ .

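### More than one surgeon chose the wire configurations, but the between-configuration tests take no account of operator; surgeon differences, if present, could appear as configuration differences

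*Combined protocol and SAP*

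**What the plan says.** Study Protocol describes a retrospective cohort of 100 children with Gartland type 3 fractures: "the patients were divided into 5 groups according to the configurations of the K-wires in fixation". Nothing was randomised.

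Surgical technique refers to surgeons in the plural and leaves the choice of configuration to them: "Surgeons decided on the number and configuration of pins used in the intraoperative period". Three guiding factors are given:

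- fluoroscopy: "They decided on the other KW in the intraoperative period according to the flexion-extension fluoroscopy images after the first KW"
- stability: "The pin number and orientation were determined entirely according to the configuration to achieve fixation stability during surgery"
- swelling: where the medial epicondyle could not be felt, "the use of a lateral pin is preferred to avoid the risk of ulnar nerve injury"

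None of these comes with a threshold or an algorithm. The number of surgeons, their caseloads and the configurations each one used are not stated.

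Statistical results lists the tests. For quantitative outcomes, "Kruskal Wallis test was used for not normally distributed three and upper groups quantitative data comparison", with Mann-Whitney to find which groups differ and Fisher-Freeman-Halton for qualitative data. Friedman, Wilcoxon and marginal homogeneity tests cover within-patient comparisons. No stratification, regression, clustering or surgeon variable appears, and Results reports nothing by surgeon.

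**The concern.** The operating surgeon is linked to both sides of the comparison. The surgeon carries out the closed reduction, which shapes postoperative alignment, and also settles the wire configuration. If a surgeon who favours one configuration also tends to obtain better or worse alignment, that configuration inherits the difference even when it has no effect of its own. The unstratified tests cannot tell the two apart.

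This is separate from confounding by fracture severity. With identical fractures, operator habit and skill could still link configuration to outcome.

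What is at stake is mainly one result. Baumann angle (BA) on the first postoperative day is the only outcome reported to differ between configurations (p = 0.015). It did not differ before surgery or at final control. Alignment on day 1 is a plausible place for operator differences to show. Surgeon effects could also hide a real configuration difference behind the null results, but that has not been quantified here.

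**Working it through.** The documents give no power, effect-size or operator figure, so there is nothing of the plan's own to reproduce. The check is how far the planned five-group test departs from 5% when configuration has no effect.

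**Inputs from the documents.** N = 100; five groups; unadjusted Kruskal-Wallis; significance at 0.05 (0.01 is also named).

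**Assumed inputs, because the text does not give them.** Group shares 40/30/8/12/10%; 4 or 8 surgeons; share of outcome variance due to surgeon (ICC) 0, 0.05, 0.10 or 0.20; preference π = 0, 0.3, 0.5 or 0.7.

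**Model.** For child i treated by surgeon s,

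y_i = u_s + e_i, with Var(u_s) = ICC and Var(e_i) = 1 − ICC.

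The child's configuration is the surgeon's favourite with probability π; otherwise it is drawn from the overall shares. Configuration does not enter y, so every rejection is a false positive.

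**What π means.** A favourite with overall share 0.40 makes up π + (1 − π) × 0.40 of that surgeon's cases:

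- π = 0.3: 0.3 + 0.7 × 0.40 = 0.58
- π = 0.5: 0.5 + 0.5 × 0.40 = 0.70
- π = 0.7: 0.7 + 0.3 × 0.40 = 0.82

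**What the ICC means.** The surgeon SD is the outcome SD × √ICC. Results gives an SD of 3.45 degrees for carrying angle on the operated side, so the surgeon SD would be 3.45 × √0.05 = 0.77, 3.45 × √0.10 = 1.09 and 3.45 × √0.20 = 1.54 degrees. These are modest differences between operators.

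**False-positive rate of the five-group Kruskal-Wallis test, nominal 5%:**

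| Surgeons | Preference π | ICC 0.05 | ICC 0.10 | ICC 0.20 |
|---|---|---|---|---|
| 4 | 0.3 | 7% | 7% | 9% |
| 4 | 0.5 | 8% | 12% | 18% |
| 4 | 0.7 | 11% | 17% | 31% |
| 8 | 0.3 | 5.5% | 6% | 7.5% |
| 8 | 0.5 | 6% | 8% | 13% |

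With π = 0 at any ICC, or ICC = 0 at any π, the rate is about 4-5%. Repeat runs agree to within about two percentage points.

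**Second model.** Here there are 3 or 5 surgeons, average shares 35/30/5/20/10%, and each surgeon's mix of configurations varies at random around those shares. The ranges run over 3 and 5 surgeons.

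| Preference | ICC 0.05 | ICC 0.10 | ICC 0.20 |
|---|---|---|---|
| None | 4.1-4.9% | 3.5-5.1% | 3.6-4.8% |
| Moderate | 6.6-7.0% | 9.6-10.3% | 14.3-17.7% |
| Strong | 10.7-12.7% | 18.2-21.1% | 32.9-35.8% |

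The pattern is the same: inflation needs surgeons to differ in outcome and also in the configurations they use.

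**With surgeon in the analysis.** A k-group rank test stratified by surgeon holds about 3-5% under the first model. A rank model with surgeon as a fixed effect holds 3.5-5.7% under the second.

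**Which tests are affected.** Only those that compare configurations. The preoperative-to-postoperative and operated-to-uninjured comparisons are made within the child and are much less exposed.

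**The case against.** The strongest reply is that the documents attribute the choice to the fracture and never to the surgeon's habit. The first wire was always lateral, later wires followed the fluoroscopy, swollen arms led to a preference for lateral wires, and wire diameter followed age and cortical thickness. Acceptable reduction had stated radiographic criteria. The text also does not say that one surgeon decided alone for each child. This limits how much discretion can be assumed. It does not remove it, because the working standard is that "The surgeons who managed the operation used an adequate number of pins to fix the fracture with sufficient stability for all patients", and neither adequacy nor sufficiency is defined.

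A reader might go further and infer that correlation among one surgeon's patients makes the p-values invalid. The documents do not support that. Correlation within surgeon does not by itself inflate the Kruskal-Wallis test: without a difference in configuration use, the rate stays near 5%. The documents show neither a difference in use nor a difference in outcome between surgeons.

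A reader might also infer that the day-1 BA difference is a surgeon effect. The evidence is mixed. The stated reduction criteria are the anterior humeral line (AHL) and the humeral capitellar angle (HCA), and neither differed between groups on day 1. If reduction quality varied by operator, those measures should be exposed too. On the other side, BA was not among the criteria, so it may have been freer to vary. Neither argument settles the matter.

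Finally, Surgical technique says that most patients received one of two crossed configurations, so the other three groups together hold fewer than half of the 100 children. Strata by surgeon may be sparse. This objection stands, and it is why the stratified test should be added to the planned tests rather than replace them.

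**Conclusion.** The concern holds as a conditional one. It is established that more than one surgeon operated, that they chose the configuration during surgery without a measurable rule, and that no between-configuration test accounts for operator. Whether this distorted any result is unknown.

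The inflation figures illustrate what could happen; they do not estimate what did. They rest on assumed surgeon numbers, ICC, preference and group shares. They shrink with more surgeons and weaker preferences, and vanish if surgeons used the configurations in the same proportions or had the same outcomes. The day-1 BA result is the one whose interpretation depends on the answer. Until operator has been examined, it should not be read as an effect of configuration. The change is worth making because a single table would show whether surgeons differed in configuration use.

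**What to change.** 1. Take the operating surgeon from the operative note where it is recorded. State the number of surgeons and tabulate surgeon by configuration.
2. Where overlap allows, add a sensitivity analysis of the between-configuration comparisons of BA, HCA, carrying angle, flexion and extension. Use either a k-group rank test stratified by surgeon (van Elteren or Cochran-Mantel-Haenszel rank-score type) or a rank model with surgeon as a fixed effect. Keep the planned tests as the main analysis. Avoid pooling many low-volume surgeons into one stratum, since that brings back part of the confounding.
3. If overlap is too small, state that surgeon and configuration cannot be separated, and do not attribute the day-1 BA difference to configuration.

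The cost is one variable from existing records, if it is retrievable, and a re-run of a few tests. Precision will fall, because surgeons who used a single configuration contribute nothing to the stratified test, and some strata may be too sparse to use. Adjusting for surgeon does not remove confounding by fracture stability or swelling, which needs its own treatment or a stated limitation.

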### ***Statistical results***

Statistical analysis was performed with NCSS ( Number Cruncher Statistical System) 2007 (Kaysville, Utah, USA). Many Whitney U test was used for descriptive statistical methods evaluation (average, standard deviation, median, frequency, ratio, minimum, maximum) and not normally distributed data comparison. Kruskal Wallis test was used for not normally distributed three and upper groups quantitative data comparison. Mann Whitney U test was used for the definition of the different groups. Friedman test was used for the comparison of intragroup not normally distributed parameters and the Wilcoxon Signed Ranks test and Marginal Homogeneity test was used for evaluation of binary comparison. Fisher-Freeman-Halton test was used for qualitative data comparison. P values were considered statistically significant when  $p < 0.01$  and  $p < 0.05$ .

